## 1. INTRODUCTION AND RATIONALE

Diabetes Mellitus (DM), Atherosclerotic Cardiovascular Disease (ASCVD), Metabolic Syndrome (MetS) and Obstructive Sleep Apnea Syndrome (OSAS) are major health problems (1-3). However due to the absence of symptoms and/or disease-related knowledge, the pathology of DM, ASCVD, MetS and OSAS often goes undetected. Approximately one-third of the people with DM are not aware of their status (17). Another study has shown that the onset of DM appears approximately 4 to 7 years before clinical diagnosis (18). Research in Dutch OSAS patients showed that in 66% of the patients it took ≥4 years before they were diagnosed with OSAS (4). Therefore, risk indicators for DM, ASCVD, MetS and OSAS are needed and proposed (4-8). In this respect the onset of several oral pathologies might be indicative.

Many studies demonstrate the association between oral diseases and DM and/or ASCVD (9, 10). The most observed chronic oral disease is periodontitis. For MetS and OSAS this association is less clear (8). However different studies have suggested an association between periodontitis and MetS (14-16) or between periodontitis and OSAS (8, 19). Periodontitis is a common chronic multifactorial inflammatory disease of the supporting structures of the teeth (root cementum, gingiva, periodontal ligament and alveolar bone). This condition is initiated and sustained by an aberrant host immune response against resident bacterial biofilms on the teeth and the tooth roots (11). Although the relative contribution of several causal factors may vary among patients, the uncontrolled inflammatory response upon bacterial accumulation seems the major factor determining the onset and/or progression of the periodontitis (12). In this respect, an increased proinflammatory state caused by processes like atherosclerosis and metabolic dysregulation might contribute to the onset and/or progression of periodontitis. Therefore periodontitis could be considered as an early sign of an underlying vascular and/or metabolic pathology (13). With this knowledge, it has been suggested that dentists could help to screen for DM, the risk of ASCVD, MetS and the risk of OSAS.

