7.8 Drug accountability

### 8. METHODS

### 8.1 Study parameters/endpoints

### 8.1.1 Main study parameter/endpoint

To investigate, within a dental setting, the differences between subjects with and without periodontitis:

- The prevalence of preDM and DM (established cut-off values for HbA1c, appendix 1 and 2 (7))

- The 10-year-risk of ASCVD ("10-year-risk" chart, appendix 3 (20))
- The prevalence of MetS (diagnostic criteria of NCEP ATP III, appendix 4 (21))
- The risk of OSAS (OSAS risk questionnaire (22))

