- Consecutive plasma finger stick procedure (HemCol, Labonovum B.V.) for measuring biomarkers: HbA1c, total cholesterol, LDL-C, HDL-C, triglycerides, Creactive protein (CRP), creatinine. A drop of blood is obtained with a finger stick (Greiner Bio-one Safety Lancet) and collected in a collection tube. The collection tube is sent to the laboratory for analysis by regular mail. (extra procedure)

Ad 5. The questionnaire for demographic characteristics contains a question about the ethnicity of the subject. The ethnicity is an important factor that is associated with DM and ASCVD. According to the NHG standards, the Turkish, Moroccan or Surinam-Hindustan origin is one of the risk factors for the screening of DM (24). Furthermore, it is known that ethnic differences have an influence on the HbA1c value. Factors such as differences in hemoglobin glycation, red cell survival or nonglycemic genetic determinants are being explored as determinants (25).

People of the Dutch population with a Turkish, Moroccan and Surinam-Hindustan origin have more often DM than people with a Dutch origin (26, 27). Also the prevalence of cardiovascular complications in diabetes patients is higher in people from these ethnic minorities, especially from Surinam-Hindustan. Cardiovascular diseases were more often diagnosed in people of Turkish origin compared to people of Dutch origin (28). Our study population in Amsterdam and surrounding areas has a

variety of different ethnic groups. Because ethnicity is one of the factors, related to DM and ASCVD, it has to be taken into account as a variable when measuring the biomarkers for DM and ASCVD.

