### NL62337.029.17 / ParoSysACTA Periodontitis as signal for an underlying disease

### **10. STATISTICAL ANALYSIS**

The prevalence of (pre)DM and MetS, the 10-year risk of ASCVD and the risk of OSAS will be presented in tables. First, one table will be generated describing the background variables, blood chemistry and demographic characteristics. Secondly, the prevalence of (pre)DM and MetS, the 10-year-risk of CVD and the OSAS risk will be reported in patients with and without periodontitis.

According to the ADA guidelines HbA1c values will be classified as normal (<5.7% [<39 mmol/mol]), preDM (5.7-6.4% [39-47 mmol/mol]) and DM (≥6.5% [≥48 mmol/mol]) (7).

The 10-year risk of ASCVD will be assessed with help of the risk table from the Dutch guideline on cardiovascular risk management (CVRM) according to the standards of the Dutch College of General Practitioners (NHG) (20). The NHG standards are derived from European Society of Cardiology guidelines and modified to the Dutch situation (6).

According to the NCEP ATP III guidelines MetS is present if three of the 3 or more of the five criteria are met: elevated waist circumference over  $\geq$  102 cm (men) or  $\geq$  88 cm (women), triglyceride (TG) level over  $\geq$  1.7 mmol/L or being on drug treatment for elevated TG, high density lipoprotein cholesterol (HDL-C) level less than < 1.03 mmol/L (men) or < 1.3 mmol/L (women), blood pressure over 130/85 mmHg or on antihypertensive drug treatment, and blood glucose level over  $\geq$  5/6 mmol/L (21).

The OSAS risk is calculated with help of a new questionnaire (PhilipsQ) which is constructed from body measurements (sex, age, BMI, neck circumference) and the most predictive questions of the following OSAS and sleep questionnaires: Berlin Questionnaire (BerlinQ), STOP Questionnaire (STOPQ) and Athens Insomnia Scale (AIS). An algorithm is developed to compute the individual estimated probability (p) that a subject will have OSAS: p(OSAS) = 1 / (1+e-X), where  $X = -6.322 + 2.828 \times AIS + 2.745 \times STOPBANGQ$  High + 0.965 × STOPBANGQ Intermediate + 4.640 × BerlinQ High + 1.584 × BerlinQ Intermediate + 0.790 × Age + 0.810 × BerlinQ Q-5. The final cutoff values were determined by exploratory logistic regression analyzes. The risk of OSAS will be classified as low (p[OSAS] < 35%), intermediate (p[OSAS] = 35-55%) and high (p[OSAS] > 55%) (22).

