The missing data from included subjects will be imputed using the expectationmaximization method. Background variables, blood chemistry and demographic data between cases and controls will be analysed by Chi-analyses or t-tests where applicable. The primary and secondary outcome variables will be analysed both by univariate analysis and multivariate analysis (multiple logistic regression). The data will be analysed on an intention-to-treat basis (ITT).

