### **10.1 Primary study parameter(s)**

The cases and controls are a priori defined by inclusion and exclusion criteria. The STROBE guideline will be followed and a flow diagram will be generated of how many individuals have been screened, invited to participate, included and analysed (29). All initially included study subjects will form part of the data analysis (intention to treat). Type I error will be controlled by including a sufficient number of cases and controls to avoid multiplicities and to apply Bonferroni corrections where applicable. Secondly, we have determined the minimal sample size on the basis of an appropriate power calculation (see chapter 4.4).

The prevalence of (pre)diabetes, the 10-year risk of ASCVD, the prevalence of MetS and the prevalences of OSAS risks (categorical variables) within the study population will be compared with parametric and non-parametric tests (ANOVA and  $Chi^2$ -test). Where applicable, analyses will be corrected for multiple testing (Bonferroni). The significance level will be set to p<0.05.

The prevalence of (pre)DM among cases and controls will be firstly reported without adjustment of any of potential covariates. In a second exploratory analysis we will adjust the prevalence for general and diabetes and ASCVD related characteristics of the study population: sex, age, ethnicity (origin of parents), education level, smoking habits, relatives with DM, history of periodontal treatment, diagnosis of hypertension, diagnosis of hypercholesterolemia, diagnosis of DM and the BMI, amount of physical activity.

The 10-year risk of ASCVD will be calculated according to the algorithm from the ESC guidelines, which is adapted to the Dutch situation. No further adjustments will be done.

The prevalence MetS will be calculated according to the criteria of the NCEP ATP III guidelines. No covariates will be included.

The risk for OSAS will be assessed by the OSAS questionnaire. No further adjustments will be done. However, the results will be explored in relation to having periodontitis, the

background characteristics, the blood chemistry outcomes and having (pre)diabetes and the 10-year risk for ASCVD.

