### 11.2 Recruitment and consent

### Patients with periodontitis

Patients with periodontitis, referred to the department of Periodontology (ACTA), will receive an information letter about the study from their dental practitioner (of ACTA) at least 1 week before their visit to the periodontal clinic. The dental practitioner is informed by the researcher about the study and the recruitment of patients. During the appointment, patients will be asked by the dental practitioner whether they want to participate with the study. Patients can give consent. The terms of the consent and when it was obtained will be documented in the case record form. After the informed consent, the dental practitioner or researcher will fill in the questionnaires with the patients and use the finger stick analysis.

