### Control subjects

Patients, visiting the dental clinic at ACTA for a regular dental checkup, will receive an information letter about the study from their dental practitioner (of ACTA) at least 1 week before their visit to the dental clinic. The dental practitioner is informed by the researcher about the study and the recruitment of patients. The dental practitioner performs the dental checkup. If the patient meets the inclusion criteria (see 8.3 Study procedures), then he/she will be asked by the dental practitioner (of ACTA) whether he/she wants to participate with the study. Patients can give consent. The terms of the consent and when it was obtained will be documented in the case record form. After the informed consent, the researcher will fill in the questionnaires with the patients and use the finger stick analysis.

Before being admitted to the clinical study, the patient must consent to participate after the nature, scope and possible consequences of the clinical study have been explained in an information letter understandable to him/her. In addition to the standard requirements that physicians are currently obliged to observe when providing information, all points on the information letter must be covered. The investigator will not undertake any investigation specifically required only for the clinical study until valid consent has been obtained. If the patient does not wish to know the result of the finger stick procedure, then he/she will not be included in the study.

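### Missing values are to be filled by expectation-maximization with no random draws, pooling or model stated; one conditional-mean fill would generally understate DM prevalence and make the DM difference depend on missingness by group

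*Combined protocol and SAP*

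**What the plan says.** Section 10 deals with missing data in one sentence: "The missing data from included subjects will be imputed using the expectationmaximization method". Neither there nor elsewhere do the documents state how many datasets are created, whether a random residual is added, which variables enter the model, whether HbA1c is imputed as a value or as a class, or how the variance allows for imputation.

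Section 10 also sets the classes: "According to the ADA guidelines HbA1c values will be classified as normal" below 39 mmol/mol, preDM from 39 to 47, and DM from 48 upwards. Section 10.1 defines the analysis set: "All initially included study subjects will form part of the data analysis (intention to treat"). Classes are compared by Chi-square and ANOVA at p<0.05, with logistic regression added in section 10. The aim in section 8.1.1 is "To investigate, within a dental setting, the differences between subjects with and without periodontitis".

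HbA1c comes from a finger-stick sample. Section 8.3 says: "The collection tube is sent to the laboratory for analysis by regular mail". No expected missing rate is given.

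**The concern.** Expectation-maximization estimates parameters. When it is used to fill a dataset, a common product is one completed dataset with each gap set to its conditional mean. That is harmless for some purposes but not for a prevalence defined by an upper-tail cut-point. Conditional means lie close to the centre, DM is the tail, and so almost no filled subject is classed as DM. Each group then loses DM cases in proportion to its missing share, and the between-group difference depends partly on who has more gaps.

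The second problem is precision. Filled values enter the Chi-square test as if measured, so the test ignores the uncertainty of the fill. If periodontal group is in the fill model, the gaps in a group are filled around that group's own estimated mean. Near a cut-point in the middle of the distribution, this can move whole blocks of filled subjects to one side.

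**Working it through.** **The plan's own figure.** Section 4.4 sizes the study on DM of 8.5% without periodontitis and 18.1% in severe periodontitis, with 90% power. Pooled-variance formula, two-sided 5%, no continuity correction, mean rate 13.3%:

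n = [1.960·√(2·0.133·0.867) + 1.282·√(0.085·0.915 + 0.181·0.819)]² / 0.096² = 260.9, that is 261 per group.

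The stated 261 is reproduced and this point does not affect it.

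**Inputs from the documents.** Pilot DM rates are 8.5% (none), 9.9% (mild/moderate) and 18.1% (severe), with equal groups of 261. All periodontitis: (9.9 + 18.1)/2 = 14.0%. True difference: 14.0 − 8.5 = 5.5 points, with standard error √(0.085·0.915/261 + 0.140·0.860/522) = 2.3 points.

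**Assumptions, not in the documents.** Missing share m of 5 to 20%, missing completely at random within group; normal HbA1c filled at its conditional mean; predictors explaining R² = 0.1 to 0.3 of its variance; pilot rates, reported for new cases, taken as all DM.

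**Step 1: how many fills reach 48.** For a group with DM rate p, a filled value is at or above the cut-off with probability f = 1 − Φ(z/√R²), where z = Φ⁻¹(1 − p).

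| Group | f at R² = 0.1 | f at R² = 0.3 |
|---|---|---|
| None (8.5%) | <0.01% | 0.6% |
| Mild/moderate (9.9%) | <0.01% | 0.9% |
| Severe (18.1%) | 0.2% | 4.8% |

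**Step 2: prevalence and difference after filling.** Expected prevalence = (1 − m)p + m·f.

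| Missing, controls / periodontitis | With vs without (true 5.5) | Severe vs none (true 9.6) |
|---|---|---|
| 5% / 5% | 5.2–5.3 | 9.1–9.3 |
| 10% / 10% | 5.0–5.2 | 8.7–9.1 |
| 20% / 20% | 4.4–4.9 | 7.7–8.5 |
| 20% / 5% | 6.5 | 10.4–10.5 |
| 5% / 20% | 3.1–3.7 | 6.4–7.3 |

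Example with no fill reaching 48, at 20%/5%: 0.140·0.95 − 0.085·0.80 = 0.133 − 0.068 = 6.5 points.

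**Step 3: when the difference is overstated.** This needs m₀(p₀ − f₀) > m₁(p₁ − f₁). If no fill reaches 48, control missingness must exceed 14.0/8.5 = 1.65 times that in all periodontitis, or 18.1/8.5 = 2.13 times that in severe. At R² = 0.3 the ratios fall to (14.0 − 2.87)/(8.5 − 0.61) = 1.41 and (18.1 − 4.80)/(8.5 − 0.61) = 1.69.

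**Step 4: tests under no difference.** Simulation with 261 per group, a common DM rate of (8.5 + 9.9 + 18.1)/3 = 12.2%, group in the fill model, and normal HbA1c (SD 5, 7 or 10) or lognormal HbA1c. Rejection rates of the nominal 5% Chi-square, with versus without:

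| Missing, controls / periodontitis | DM (≥48) | (pre)DM (≥39) |
|---|---|---|
| 10% / 10% | about 5–6% | about 5–10% |
| 20% / 20% | 4–6% | 6–17% |
| 10% / 5% | 4–7% | 6–10% |
| 20% / 5% | 9–13% | 8–22% |

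Complete-case tests stayed at about 4–6%. With group left out of the model, ≥39 was about 5% at equal missingness, but the ≥39 difference was then diluted (SD 7: 10.7 to 9.6 points at 10% missing).

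**Step 5: known DM in the model.** Section 1 notes: "Approximately one-third of the people with DM are not aware of their status". With a diagnosis flag for the other two thirds, the loss at equal 10% falls from 0.3–0.5 to about 0.15 points, and the DM test at 20%/5% falls to about 6%. At SD 7 the ≥39 test still rejects 6–11% at equal 10%.

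**The case against.** **The reading is conditional.** The plan does not say that the fill is a single conditional mean or that HbA1c is filled on its continuous scale. Both are inferences, and the downward direction needs both. With known DM in the model the direction could even reverse, because diagnosed subjects whose HbA1c is below 48 might be filled as DM. If 50 to 90% of diagnosed subjects are at or above the cut-off, reversal needs a diagnosed share above about 14–46% without periodontitis, or 24–62% in severe. This stands as a limit on the claim.

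**The DM effect is small when missingness is similar.** At equal 5 to 10% missing the shift is at most about 0.5 points against a standard error of 2.3, and the DM test holds its level. This stands.

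**The ≥39 inflation is not general.** At SD 5 and equal 10% missing it is about 5 to 6%, and it disappears at equal missingness if group is left out of the model. Treating (pre)DM as one cut at 39 is itself a reading of the plan. So the test can reject too often; it need not.

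**Unequal missingness is not shown.** A reader might infer it from the staffing in section 11.2. For patients: "After the informed consent, the dental practitioner or researcher will fill in the questionnaires with the patients and use the finger stick analysis". For controls: "After the informed consent, the researcher will fill in the questionnaires with the patients and use the finger stick analysis". That is a difference in who collects the data. Section 8.3 applies the same finger stick, tube, mailing and laboratory to everyone at one visit. The documents support neither a fourfold imbalance nor a prediction of which group has more gaps.

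**More detail would be enough.** Specifying the method would remove the ambiguity. But if the method specified is one fill, the bias and missing variance remain, so a better method is worth asking for.

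**Conclusion.** The concern holds in conditional form. As written, the plan carries no imputation uncertainty into its tests. If HbA1c is filled once at its conditional mean, DM prevalence is generally understated, and the with-versus-without difference moves with missingness by group: from 5.5 points to 5.0–5.2 (equal 10%), 6.5 (20%/5%) or 3.1–3.7 (5%/20%).

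It would be too strong to say that the plan inflates the DM comparison. Overstatement needs control missingness above about 1.65 times that in periodontitis (about 1.4 times at R² = 0.3), and DM test levels of 9–13% appeared only with clearly unequal missingness. With similar, modest missingness the DM result is slightly diluted and its test stays near 5%. The ≥39 test is more exposed, from nominal to about 10% at equal 10% missing.

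All sizes rest on assumed missing shares, HbA1c distributions and R². MetS, ASCVD and OSAS were not computed. The change should be made because it is cheap and removes the dependence on missingness patterns that cannot yet be known; confidence is medium.

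**What to change.** Replace the imputation sentence in section 10 with a paragraph that specifies:

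- multiple imputation, for example 20 or more datasets, of the raw components: HbA1c, lipids, blood pressure, waist, and the measurements and items behind the OSAS score;
- an imputation model containing periodontal group (none, mild/moderate, severe), known DM diagnosis, the other outcomes and the covariates of section 10.3;
- DM/preDM, MetS, ASCVD and OSAS classes derived after imputation;
- pooling by Rubin's rules, with group tests from pooled logistic or multinomial models;
- missingness reported by variable and periodontal group, and complete-case results as a sensitivity analysis.

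In simulation with 20 datasets, the severe-versus-none DM difference came back as 9.5–9.7 points (truth 9.6) at 10%/10%, 20%/5% and 5%/20% missing. Null rejection at 20%/5% was 3.5%, against 9% for one fill.

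The cost is one paragraph and modest programming, including pooled versions of the planned tests. Intervals widen slightly: the severe-versus-none standard error at 10% missing is 3.07–3.09 points, against 2.81–2.83 with one fill. The test is slightly conservative, with simulated null rejection of 2–4% at ≥48 and 3–5% at ≥39.

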### **10.1 Primary study parameter(s)**

The cases and controls are a priori defined by inclusion and exclusion criteria. The STROBE guideline will be followed and a flow diagram will be generated of how many individuals have been screened, invited to participate, included and analysed (29). All initially included study subjects will form part of the data analysis (intention to treat). Type I error will be controlled by including a sufficient number of cases and controls to avoid multiplicities and to apply Bonferroni corrections where applicable. Secondly, we have determined the minimal sample size on the basis of an appropriate power calculation (see chapter 4.4).

The prevalence of (pre)diabetes, the 10-year risk of ASCVD, the prevalence of MetS and the prevalences of OSAS risks (categorical variables) within the study population will be compared with parametric and non-parametric tests (ANOVA and  $Chi^2$ -test). Where applicable, analyses will be corrected for multiple testing (Bonferroni). The significance level will be set to p<0.05.

The prevalence of (pre)DM among cases and controls will be firstly reported without adjustment of any of potential covariates. In a second exploratory analysis we will adjust the prevalence for general and diabetes and ASCVD related characteristics of the study population: sex, age, ethnicity (origin of parents), education level, smoking habits, relatives with DM, history of periodontal treatment, diagnosis of hypertension, diagnosis of hypercholesterolemia, diagnosis of DM and the BMI, amount of physical activity.

The 10-year risk of ASCVD will be calculated according to the algorithm from the ESC guidelines, which is adapted to the Dutch situation. No further adjustments will be done.

The prevalence MetS will be calculated according to the criteria of the NCEP ATP III guidelines. No covariates will be included.

The risk for OSAS will be assessed by the OSAS questionnaire. No further adjustments will be done. However, the results will be explored in relation to having periodontitis, the

background characteristics, the blood chemistry outcomes and having (pre)diabetes and the 10-year risk for ASCVD.

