# 2. OBJECTIVES

Primary Objective:

To investigate, within a dental setting, the differences between subjects with and without periodontitis in:

- The prevalence of preDM and DM (established cut-off values for HbA1c, appendix 1 and 2 (7))
- The 10-year-risk of ASCVD ("10-year-risk" chart, appendix 3 (20))
- The prevalence of MetS (diagnostic criteria of NCEP ATP III, appendix 4 (21))
- The risk of OSAS (OSAS risk questionnaire (22))

Secondary Objective(s):

- To investigate the differences in (pre)DM prevalence, 10-year-risk of ASCVD, MetS prevalence and OSAS risk between mild/moderate and severe periodontitis patients

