### 4.4 Sample size calculation

The calculation of the sample size was based on a  $Chi^2$ -test having an  $\alpha$ <0.05 with 90% power and using the prevalence of diabetes of two groups (without periodontitis: 8.5%, severe periodontitis: 18.1%)(13). The required sample size is a minimum of 261 subjects per group.

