# APPENDIX 3: The 10-year-risk chart of ASCVD (for patients without known ASCVD) (30)

	Vrouwen									Mannen											
SBD		Niet	-rook	ster			Re	ookst	ter		Leef-	Niet-roker					Roker				
180	35	38	41	43	44	47	50	>50	>50	>50	tijd	>50	>50	>50	>50	>50	>50	>50	>50	>50	>50
160	28	31	33	35	36	38	41	44	46	48		45	48	>50	>50	>50	>50	>50	>50	>50	>50
140	22	24	26	28	29	31	33	36	38	39	70	37	40	42	44	46	49	>50	>50	>50	>50
120	18	19	21	22	23	25	27	29	30	32		30	32	34	36	38	40	43	45	48	50
180	14	17	20	24	30	27	32	37	45	>50		25	30	36	44	>50	45	>50	>50	>50	>50
160	10	12	14	17	21	19	22	27	32	39		18	21	26	32	40	33	39	47	>50	>50
140	7	8	10	12	15	14	16	19	23	28	65	12	15	18	23	29	23	28	34	42	>50
120	5	6	7	9	11	10	11	14	17	20		9	11	13	16	21	17	20	24	30	38
180	10	12	15	18	23	20	23	28	34	42		22	26	32	40	50	40	48	>50	>50	>50
160	7	8	11	13	16	14	17	20	24	30		15	19	23	29	36	29	35	42	>50	>50
140	5	6	7	9	12	10	12	14	17	21	60	11	13	16	20	26	20	25	30	38	47
120	4	4	5	7	8	7	8	10	12	15		8	9	12	15	19	14	18	22	27	34
180	5	6	8	10	12	10	12	15	18	22		13	16	20	26	32	25	31	38	47	>50
160	4	4	5	7	9	7	8	10	13	16		10	12	15	18	23	18	22	27	34	43
140	3	3	4	5	6	5	6	7	9	11	55	7	8	10	13	17	13	16	19	24	31
120	2	2	3	3	4	4	4	5	6	8		5	6	7	9	12	9	11	14	17	22
180	2	3	4	5	6	5	6	7	9	11		8	10	12	15	20	15	18	23	28	36
160	2	3	3	3	4	3	4	5	6	8		6	7	9	11	14	11	13	16	20	26
140	1	1	2	2	3	2	3	3	4	6	50	4	5	6	8	10	7	9	12	15	19
120	1	1	1	2	2	2	2	2	3	4		3	3	4	6	7	5	7	8	10	13
180	1	1	1	1	1	1	1	1	2	2		3	3	4	6	7	5	6	8	10	13
160	<1	<1	1	1	1	1	1	1	1	2		2	2	3	4	5	4	4	6	7	9
140	<1	<1	<1	1	1	<1	<1	1	1	1	40	1	2	2	3	4	3	3	4	5	7
120	<1	<1	<1	<1	<1	<1	<1	1	1	1		1	1	2	2	3	2	2	3	4	5
	4	5	6	7	8	4	5	6	7	8		4	5	6	7	8	4	5	6	7	8
			Rati	o tot	aal eł	olest	erol/	HDL						Rati	o tot	aal ch	olest	erol/	HDL		

Tabel 1. Risicotabel: 10-jaarsrisico op ziekte of sterfte door HVZ voor patiënten zonder HVZ

< 10% risico op ziekte of sterfte door HVZ; leefstijladviezen indien daar aanleiding voor is, zelden medicamenteuze behandeling.

10% tot 20% risico op ziekte of sterfte door HVZ; leefstijladviezen, medicamenteuze behandeling alleen bij risicoverhogende factoren en SBD > 140 mmHg en/of LDL > 2,5 mmol/l.

≥ 20% risico op ziekte of sterfte door HVZ; leefstijladviezen, medicamenteuze behandeling als SBD > 140 mmHg en/of LDL > 2,5 mmol/l.

Het risico bij patiënten met DM of RA kan worden geschat door bij de actuele leeftijd van de patiënt 15 jaar op te tellen.

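### Section 10.1 credits type I error control partly to sample size and leaves the Bonferroni family undefined; four defined primary tests under Holm would close the gap, with a power gain over Bonferroni of 0 to 10 points per outcome.

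*Combined protocol and SAP*

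**What the plan says.** Sections 2 and 8.1.1 list four primary outcomes: (pre)diabetes, 10-year ASCVD risk, metabolic syndrome and OSAS risk. The objective concerns "the differences between subjects with and without periodontitis in" these outcomes, and no outcome is ranked above another.

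On error control, section 10.1 states: "Type I error will be controlled by including a sufficient number of cases and controls to avoid multiplicities and to apply Bonferroni corrections where applicable". It later repeats the commitment ("Where applicable, analyses will be corrected for multiple testing (Bonferroni") and adds: "The significance level will be set to p<0.05". It does not say which tests form the family, how many there are, or what adjusted level applies. Section 10 and section 10.1 between them name Chi-square tests, ANOVA, and univariate and multivariate analyses. Section 10.2 repeats the same procedures for severe versus mild/moderate periodontitis.

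Section 4.4 sizes the study at alpha "<0.05 with 90% power and using the prevalence of diabetes of two groups", namely 8.5% without periodontitis and 18.1% with severe periodontitis. The result is 261 per group.

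**The concern.** The first statement is wrong as statistics. Enrolling more subjects raises power. It neither changes the false-positive rate of a test run at a fixed level nor removes multiplicity when several outcomes are tested.

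What remains is Bonferroni, a valid method, but qualified in a way that leaves its scope open. An analyst could hold each primary outcome to 0.0125 or to 0.05 and claim to have followed the plan, and that choice could be made after the data are seen. The hypothesis in section 1 covers all four outcomes, so a positive claim could rest on any one of them. The chance of at least one false claim is therefore the relevant error rate.

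Two things are at stake: an inflated family-wise error if the correction is not applied to the primary outcomes, and unnecessary loss of power if it is applied in single-step form when a uniformly better procedure needs no extra data or assumptions.

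**Working it through.** **1. Reproduce the plan's figure.** Inputs from section 4.4: p1 = 0.085, p2 = 0.181, power 90%, alpha 0.05 (taken as two-sided). Mean rate = 0.133.

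n = [z(α/2)·√(2·0.133·0.867) + z(0.90)·√(0.085·0.915 + 0.181·0.819)]² / 0.096²
= [1.960·0.4802 + 1.2816·0.4754]² / 0.009216 = 260.9, so 261.

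This matches exactly. The match needs an undivided alpha of 0.05, so no multiplicity correction is built into the sample size.

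**2. Family-wise error if four tests each use 0.05.** Independent tests: 1 − 0.95⁴ = 18.5%. The documents give no correlation between the outcomes, so a common correlation is assumed. Simulation (400,000 draws of four normal test statistics) gives 17.3% at 0.3, 15.6% at 0.5 and 13.0% at 0.7.

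**3. Holm against Bonferroni over the same four tests.** Bonferroni compares every p-value with 0.0125. Holm compares the ordered p-values with 0.0125, 0.0167, 0.025 and 0.05 and stops at the first failure. With all four nulls true, both methods gave a simulated family-wise error of 4.3% to 4.9% at correlation 0 to 0.5. Holm rejected everything Bonferroni rejected in every draw.

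Power per truly different outcome, assuming each has 90% power at 0.05 and correlation 0 to 0.5:

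| Outcomes truly different | Bonferroni | Holm | Gain (points) |
|---|---|---|---|
| 1 | 77% | 77% | about 0 |
| 2 | 77% | 79–80% | about 2 |
| 3 | 77% | 82–83% | about 5 |
| 4 | 77% | 85–87% | 8–10 |

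The chance of at least one rejection is identical, because Holm's first step is the Bonferroni test.

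**4. What correction does to the stated power.** For 8.5% versus 18.1% with 261 per group:

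z = (√261·0.096 − 2.498·0.4802)/0.4754 = (1.5509 − 1.1995)/0.4754 = 0.739, so power at 0.0125 is 77.0%.

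At Holm's later steps it is 80.1% (0.0167), 84.1% (0.025) and 90.0% (0.05). Keeping 90% at 0.0125 would need 355 per group, which is 94 more per group and 3 × 355 = 1065 in total instead of 783.

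**5. The primary contrast is a different one.** With versus without periodontitis is 522 versus 261 if the two periodontitis groups are pooled. Assume a pooled diabetes rate of (9.9% + 18.1%)/2 = 14.0%, using the pilot rates quoted in section 1. The overall rate is then (261·8.5% + 522·14.0%)/783 = 12.17%, the null standard error 0.02478 and the alternative standard error 0.02299.

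- At 0.05: z = (0.055 − 1.960·0.02478)/0.02299 = 0.28, power 61%.
- At 0.0125: z = (0.055 − 2.498·0.02478)/0.02299 = −0.30, power 38%.

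**The case against.** Bonferroni is valid, and section 10.1 commits to it twice. The 0.05 threshold is compatible with it if adjusted p-values are compared with 0.05. A reader might infer that the study has no effective error control; the documents do not support that. The fair charge is that the scope of the correction is undefined, and naming the family would cure that under either method.

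It can also be said that choosing Holm is a preference. That does not stand: Holm gives the same guarantee, never rejects less, and requires nothing further from the data. But three stronger readings should be resisted.

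- **The overlap of outcomes as the reason for Holm.** The overlap is real. For patients with diabetes or rheumatoid arthritis, Appendix 3 estimates risk by adding 15 years to age ("Het risico bij patiënten met DM of RA kan worden geschat door bij de actuele leeftijd van de patiënt 15 jaar"), and HDL-C, blood pressure and dysglycaemia or diabetes enter both ASCVD risk and metabolic syndrome. But Holm uses no correlation information either, and with all four effects real its gain falls from 10 to 8 points as correlation rises from 0 to 0.5.
- **A gain of 8 to 10 points as the expected result.** That needs all four effects to be real with 90% power each. The documents size diabetes only and give no effect sizes for the other three outcomes.
- **More power at no cost.** This is true only against Bonferroni over the same tests. Against the 90% in section 4.4, the first step still gives 77%. Simultaneous confidence intervals are also less simple than with Bonferroni.

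Finally, four is the right count only once each outcome has one test. HbA1c and OSAS risk are each classified in three levels, and several analyses are named.

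**Conclusion.** The point holds in this form. The statement that sample size controls type I error is wrong and should go. The family for Bonferroni is undefined; leaving the primary outcomes uncorrected would put family-wise error at 18.5% under independence, or about 15.6% at correlation 0.5. Over a defined family of four, Holm is the better choice, with a gain per outcome from nil to about 10 points depending on how many outcomes truly differ.

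These gains rest on equal 90% power at 0.05 and a common correlation of 0 to 0.5, both assumptions. The 77% is for diabetes in none versus severe. For the pooled primary contrast the corresponding figure is about 38%, under the assumed 14.0% rate and before any gain from Holm's later steps.

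**What to change.** In section 10.1:

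1. Delete the claim that the number of cases and controls controls type I error.
2. For each of the four primary outcomes, name one test and one with-versus-without contrast, including how the three-level classifications are handled.
3. State that these four tests form one family, tested with the Holm procedure at an overall two-sided 5%. Keep the severe versus mild/moderate comparisons as secondary and outside this family.

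In section 4.4, state that the 90% power holds only at an undivided 0.05. With 261 per group and 8.5% versus 18.1%, power is 77% at Holm's first step (0.0125), and this concerns none versus severe rather than the primary contrast.

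The cost is a short rewrite of two sections, with no change to recruitment or procedures. The downsides are less simple simultaneous confidence intervals than with Bonferroni and a less favourable stated power.
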